Abnormal chronic inflammation in the lamina propria is a typical histological characteristic but does not allow a distinction between the subtypes of MC.¹⁵ CC is characterized by a thickened subepithelial collagen layer, i.e., $> 10 \mu\text{m}$ in well-oriented biopsies cut perpendicularly to the surface,¹⁶ and lymphocytic colitis (LC) is characterized by an increased number of intraepithelial lymphocytes (IEL), i.e., ≥ 20 IEL per 100 epithelial cells. Colonic biopsies are considered normal in the absence of chronic inflammation in the lamina propria, when the number of surface epithelial cells is ≤ 5 IEL/100, and the collagen band is ≤ 5 micrometers.^{10,17}

Recent studies have shown that histological features in the individual patient are inconsistent over time, as findings of MC interchange with chronic (non-specific) inflammation or incomplete signs of MC at prior or repeat colonoscopy, and the overlap between CC and LC is significant.^{8,18,19} This histological interchange between MC subtypes and the incomplete identification of some patients have led to the introduction of a third subtype designated as incomplete MC (IC). The histological criteria for IC are an abnormally thickened collagenous band (> 5 and $< 10 \mu\text{m}$), and /or an increased number of intraepithelial lymphocytes (> 5 and < 20 per 100 epithelial cells) without reaching the thickness or number required for the diagnosis of CC or LC.¹

Epidemiologic studies show that MC is almost as common as classic IBD (i.e. Crohn's disease and ulcerative colitis).^{13,20-22} The incidence of MC appears to be rising and in some countries it may be diagnosed in 10% of patients investigated for chronic non-bloody diarrhoea, and in 20% or more of such patients older than 70 years.^{13,20} After a period of rising incidence figures, the data have been more divergent in recent studies. Incidence rates of 2.6/100,000 to 10.8/100,000 inhabitants have been reported for CC, and an annual incidence rate of 2.2 to 14 per 100,000 inhabitants for LC.^{13,20-22} Patients with MC are predominantly elderly women, and the average age at diagnosis is approximately 65 years, but a recent study shows that the age at diagnosis is increasing and a large proportion are now diagnosed in their seventies. This may be attributable to the rising of life expectancy observed over the last decades.²³ The female predominance is very clear in MC, but is less pronounced for LC than for CC.²¹

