7.2 SYMPTOMS ASSESSMENT

The symptoms will be assessed throughout 24 months (approximately every 3 months) for all patients with confirmed diagnosis of MC (any type). The symptoms include:

- Stool frequency (number of stools per day).
- Stool consistency (type of stool according to the Bristol Stool Chart – Figure 1)
- Nightly diarrhea
- Urgency (0 = no urgency, 1 = need to defecate within 30 minutes, 2 = immediate need to empty the bowel, 3 = fecal incontinence - have to go immediately to the toilette),
- Difficulties staying continent with a respective bowel movement (yes/no)
- Abdominal pain (0 = no pain, 1 = mild, 2 = moderate, 3 = severe pain)

The Bristol Stool Chart is used to monitor change in intestinal function and is widely used both in clinical practice and research. This scale classifies the form of human faeces into seven categories (figure 2).

[figure not shown]

Figure 2 – Bristol Stool Chart

During the first appointment of the study, the symptoms will be captured by the physician into the eCRF by interviewing all the eligible patients who will report to the previous 7 days. During the subsequent appointments the symptoms will **only** be recorded by the MC patients, using the patient diary. The patient diary should be completed on a daily basis for the period of 7 days before the next appointment to the specialist. The symptoms to be captured in the diary include the total number of stools and its type (according to Bristol Stool Chart) and therapies used (pharmacological/non-pharmacological) between appointments. The physician should clarify with the patient any inconsistency or missing information found in the patient diary.

The patient will be given at each appointment the necessary number of diaries to cover the period until the next scheduled appointment.

In case the patient forgets or loses the diary at one appointment, the investigator and the patient will have to estimate the number of stools and watery stools and this situation should be recorded in the eCRF (as estimated result) due to missing diary.

At each appointment, the investigator calculates the mean number of stools and of watery stools per day according to the formula:

The number of stools (any type) and watery stools in the week prior to the appointment will be divided by number of days with entries.

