9 STATISTICAL ANALYSIS

9.1 GENERAL CONSIDERATIONS

All quantitative variables will be summarized through descriptive statistics namely mean, median, standard deviation and range (minimum and maximum) and qualitative variables through absolute (n)

and relative frequencies (%) and 95% confidence intervals (if applicable). The statistical analysis will be performed through frequency tables for qualitative variables and tables with descriptive statistics for quantitative variables.

The association between two quantitative variables will be performed through Pearson correlation coefficient or Spearman correlation coefficient, in case the normality assumption is not verified.

The association of two categorical variables will be tested through the Chi-Square test or Fisher Exact test (if applicable).

The comparison of two independent samples in respect to quantitative variables will be performed through t-test for independent samples or the Mann-Whitney non-parametric test, according to the assumption validations of the statistical test (if applicable).

The proportion of patients with clinical remission and histological remission (overall, by MC subtype and colonic segment) at each data collection time points will be summarized using 95% confidence intervals.

Area under the ROC curve will be used to correlate numerical variables with binary categorical variables. A high discriminatory ability will be considered for values > 0.75 .

Repeated Measures Analysis or Generalized Estimated Equations will be used to investigate the evolution profile of clinical and histological characteristics throughout the data collection time points (time-effect).

Generalized Estimated Equations will be used to explore the association between clinical (as independent variable) and histologic features (as dependent variable) observed within-patients.

The association analysis of fecal calprotectin, EPC and EPX with clinical activity

- The association between fecal calprotectin levels EPC and EPX with clinical activity (remission/active disease) will be analyzed through Area Under the ROC Curve at each data collection time point (diagnosis and every 3 months up to month 24).

The association analysis of fecal calprotectin EPC and EPX with histological features

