9.2 SAMPLE SIZE

This study will include 300 patients with chronic diarrhea allowing the estimation of a prevalence of 10-15%^{23,37} with an error margin of less than 4.5% and with 95% confidence interval. Assuming the lowest rate of the prevalence interval (10%), approximately 30 patients with MC are expected to be followed in the prospective component study.

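### The histological time effect in section 9.1 compares a diagnosis biopsy selected for abnormality with an unselected month 24 biopsy, so for MC status, IEL and collagen it is confounded with regression to the mean

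*Protocol*

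**What the plan says.** Section 9.1 applies one time-effect analysis to both kinds of outcome: it is "used to investigate the evolution profile of clinical and histological characteristics throughout the data collection time points (time-effect"). No significance level is given for it, and section 2.3 states that there is no predefined hypothesis.

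**Histology.** Under 7.4.2, MC is confirmed only if IEL above 5 per 100 surface epithelial cells and/or a collagen layer above 5 µm is found in at least two colon segments. Only confirmed cases are followed (section 4). Histology is repeated once, at month 24 (7.1 and the appendix). Section 2.1 reports that "histological features in the individual patient are inconsistent over time". The Geboes grade is recorded but is not among the criteria for confirming MC.

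**Symptoms.** Section 7.2 has first-visit symptoms "captured by the physician into the eCRF by interviewing all the eligible patients", about the previous 7 days. For later visits, "The patient diary should be completed on a daily basis for the period of 7 days before the next appointment". Section 7.1 adds that the physician checks the diary and interviews the patient. The listed diary content is stool number, stool type and therapies.

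**Size.** Section 9.2: "This study will include 300 patients with chronic diarrhea", and "approximately 30 patients with MC are expected to be followed in the prospective component study".

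**The concern.** A test of equal means over time answers whether patients have changed only if the values being compared were obtained in comparable ways. With two histology points, the time effect is simply diagnosis against month 24. The first value had to be abnormal for the patient to be in the analysis, and the second can take any value. Ordinary biopsy-to-biopsy variation then lowers the second mean relative to the first. MC status is met by 100% at diagnosis by design and can only fall.

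Progression is a stated aim of the prospective part (sections 2.3 and 4), and the time effect is the analysis named for it. There is no comparator, and patients are treated under routine care after diagnosis. A significant result could be reported as histological improvement when some or all of it comes from how patients were chosen.

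Stool counts raise a different and conditional problem. They were not selected by a threshold on the 7-day count, since entry needs only a history of chronic or intermittent watery diarrhea. They were, however, collected differently at baseline and at follow-up.

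**Working it through.** **1. The plan's own figures.** Section 9.2 describes 300 patients as "allowing the estimation of a prevalence of 10-15" percent "with an error margin of less than 4.5% and with 95% confidence interval". The half-width is 1.96 × √(p(1−p)/300), which is 3.39 points at p = 0.10 and 4.04 points at p = 0.15. Both are below 4.5. The expected number of cases is 300 × 0.10 = 30. The plan's figures reproduce, so n = 30 is used below, with no allowance for losses by month 24.

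**2. Histology as the upper tail of a continuous score.** Assumptions, none from the protocol: a standard normal score, test-retest correlation ρ, the top 10% at the first biopsy followed, no true change, a paired t-test at two-sided 0.05.

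- Mean of the selected first value: φ(1.2816)/0.10 = 0.1755/0.10 = 1.755 SD.
- Expected change with no disease change: −(1−ρ) × 1.755.
- Variance of the change among those selected: (1−ρ)² × 0.169 + (1−ρ²), where 0.169 = 1 + 1.2816 × 1.755 − 1.755².
- Worked case, ρ = 0.9: change −0.1755; variance 0.01 × 0.169 + 0.19 = 0.1917; SD 0.438; standardized effect 0.1755/0.438 × √30 = 2.20, against a critical value of 2.045 on 29 degrees of freedom. Rejection is therefore a little over one half.

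Simulation results:

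| ρ | Mean change (SD) | False rejection | Below cut-off at second biopsy |
|---|---|---|---|
| 0.7 | −0.53 | 97% | 53% |
| 0.8 | −0.35 | 85% | 44% |
| 0.9 | −0.17 | 55% | 31% |
| 0.95 | −0.09 | 32% | 22% |

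An unselected control gave about 5%. Selecting the top 15% (about 45 cases) gave 99%, 91%, 63% and 37%.

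**3. Histology with MC as a distinct group.** Assume 30 confirmed cases from a diseased population whose mean lies D within-patient SDs above the cut-off, with between-patient SD equal to within-patient SD. False rejection is 65%, 22%, 8% and 5% at D = 0, 1, 2 and 3.

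**4. MC status as yes/no.** All changes run one way, so an exact McNemar test with k reverters has p = 2 × 0.5^k: 0.0625 at five and 0.031 at six. If the reversion rate from noise alone is 10%, 15%, 20% or 25%, the chance of at least six among 30 is 7%, 29%, 57% or 80%.

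**5. Stool counts, if the baseline is in the model.** Repeated-measures F-test, n = 30, no true change, baseline shifted by the change of method. The shifts are assumptions.

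| Shift (SD) | Within-patient correlation 0.5 | Within-patient correlation 0.7 |
|---|---|---|
| 0.1 | 6% | 8% |
| 0.2 | 14% | 20% |
| 0.3 | 28% | 47% |
| 0.5 | 71% | 94% |

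With months 3 to 24 only, rejection is about 5% throughout.

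**6. Denominator.** Sections 7.1 and 8.3.1 divide the week's stools by 7. Section 7.2 divides by the number of days with entries and accepts five or more. Fifteen stools recorded over five days give 15/5 = 3.0 per day under one rule and 15/7 = 2.1 under the other. These fall on opposite sides of the limit of 3 stools per day in 8.3.1.

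**The case against.** Several points on the other side are sound.

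- **Movement is not only downward.** A reader might infer that fluctuation can show up only as improvement. That is true of MC status alone. Section 8.3.2 provides for aggravation, incomplete colitis can move up a category, and segments normal at diagnosis can become abnormal. In the model of step 2, 24% to 39% of selected patients score higher at the second biopsy. The bias is in the mean.
- **Not every feature is selected.** The Geboes grade is not an entry criterion. Because entry is by IEL and/or collagen, one of the two may be unselected in a given patient.
- **The size depends on the model.** The documents settle neither the shape of the distribution nor the reliability, and step 3 reaches nominal error. Section 2.1 does not call the inconsistency measurement error. Some of it may be the evolution that the study means to describe, and treatment makes real change likely.
- **The clinical model may already exclude baseline.** Section 8.2 ties the time points for clinical remission to months 3 to 24, and 7.1 uses the term in its follow-up list. Section 9.1 adds diagnosis explicitly only for the biomarker analyses. Urgency, pain, nightly diarrhea and continence are not listed as diary items, and follow-up also includes an interview.
- **The aims are descriptive or exploratory**, and no passage says a time effect will be claimed as improvement.

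These points narrow the concern and make its clinical part conditional. They do not remove the selection from the diagnosis-to-month-24 comparison of MC status, IEL and collagen, because the protocol itself fixes the test, the two biopsy times and the entry rule.

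**Conclusion.** The point holds for histology in limited form. For MC status, IEL and collagen, the time effect in 9.1 is confounded with regression to the mean and can reject no change more often than 5% without any change in disease. The rate is about 32% to 97% under the upper-tail model with assumed correlation 0.95 to 0.7. It is near 5% if cases lie three or more within-patient SDs above the cut-off. Incomplete colitis borders the normal limit by definition, so at least some cases are exposed.

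A reader might infer that the test will reject regardless, or that one diagnosis value is both selected and recalled. The documents support neither. The rate depends on quantities they do not give. Histology is selected but not recalled, and stool counts are recalled but face no 7-day entry threshold.

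For stool number and type, the time effect includes a change of method only if baseline enters the model, which 9.1 leaves open. The direction of that bias is unknown. The conflict between the two denominator rules stands either way.

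**What to change.** In section 9.1:

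1. Replace the diagnosis-versus-month-24 histology time-effect test with month 24 status and its 95% CI, plus the paired cross-tabulation of diagnosis against month 24 by subtype.
2. State that the change from diagnosis includes regression to the mean and treatment under routine care, and cannot by itself be read as improvement. The cross-tabulation carries the same selection, so this sentence must accompany it.
3. State that the time effect for stool number and type is estimated on the diary visits, months 3 to 24, with change from baseline reported separately and descriptively.

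In addition, reconcile the denominator in 7.1 and 8.3.1 with that in 7.2.

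The cost is wording only; no data collection changes. What is lost is a formal test of change from diagnosis, including the first step to month 3 and the only planned test of histological change over time.

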3.2 SECONDARY OBJECTIVES

- To determine the prevalence of MC subtypes (CC, LC and IC)
- To compare the socio-demographic, clinical and histological characteristics and previous therapies of patients with confirmed diagnosis of MC (MC patients) versus patients without diagnosis of MC (non-MC patients)
- To describe the therapeutic attitude regarding MC patients over a period of 24 months
- To describe the clinical activity of MC patients over a period of 24 months.
- To describe the histological features of MC patients 24 months after diagnosis.
- To explore the association of socio-demographic, clinical and histological characteristics with clinical activity among MC patients followed for 24 months.
- To explore the association of socio-demographic, clinical characteristics with histological activity among MC patients followed for 24 months.
- To explore the correlation between the treatments used by MC patients and clinical activity.
- To explore the correlation between the treatments used by MC patients and histological activity.

- To explore the correlation between fecal calprotectin, EPC and EPX levels and clinical activity among MC patients.
- To explore the correlation between fecal calprotectin, EPC and EPX levels and histological activity among MC patients.

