- Result of colonoscopy: normal/abnormal - describe whether other findings may have caused diarrhoea (e.g., polyps > 2 cm, tumors, Crohn's disease, ulcerative colitis, ischemic colitis, other).

For patients with macroscopically normal colonoscopy:

- Date of sampling of colonic specimens (this date will correspond to the date of MC diagnosis, if confirmed).
- Date of histological assessment
- Histological evidence of MC (yes/no). The following features will be captured:
 - Geboes Index (grade for each of the colon segments: rectum, sigmoid, descending, transverse and ascending) – see Section 7.4.2.
 - Thickness of the subepithelial collagen layer (not observed, $\leq 5 \mu\text{m}$; > 5 and $< 10 \mu\text{m}$; $\geq 10 \mu\text{m}$)
 - IEL in the surface epithelium (not observed, < 5 IEL/100 surface epithelial cells, > 5 and < 20 IEL/100 surface epithelial cells, ≥ 20 IEL/100 surface epithelial cells);
- If a diagnosis of MC was not confirmed, was other diagnosis established? Yes/no - if yes, describe.

Characterization of MC patients

- MC histological assessment: location of microscopic findings (by colon segment), type of MC (lymphocytic, collagenous, incomplete colitis) - see histological assessment in section 7.4.
- Therapeutic attitude upon MC confirmation
 - Antidiarrheal medication (e.g., loperamide or diphenoxylate/atropine),
 - Bismuth subsalicylate or aminosalicylates, e.g. 5-aminosalicylic acid
 - Cholestyramine
 - Corticosteroids (budesonide, prednisolone)
 - Immunosuppressive agents, e.g. azathioprine, 6-mercaptopurine or methotrexate
 - Surgical intervention (e.g. ileostomy)
 - Other interventions (pharmacological or non-pharmacological)
- Dispensing of patient diary card to document the number of stools including the type according to Bristol stool form scale (see section 7.2) in the week prior to the next appointment. In addition, the use of additional pharmacological or other therapies will be recorded by the patient.

Follow up assessments of MC patients (as per routine practice) - month 3, 6, 9, 12, 15, 18, 21 and 24.

The following will be assessed throughout the 24-month prospective component of the study - see **Appendix**.

At every data collection time point

- Weight (kg)
- Symptoms (to be captured by the physician by checking the patient diary and interviewing the patient, referring to the previous 7 days):

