- The association between fecal calprotectin, EPC and EPX levels with histological features (collagen thickness [$\leq 5 \mu\text{m}$; $> 5 \mu\text{m}$], inflammation [Geboes grade < 3.1 ; grade ≥ 3.1] and IEL count [$\leq 5 \text{ IEL}/100$; $> 5 \text{ IEL}/100$ surface epithelial cells) will be analyzed through Area Under the ROC Curve at each data collection time point (diagnosis and month 24).

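### Section 9.1 relates the fecal markers to histology only through two-level cuts, so the analysis cannot show a graded relation that the stored ordered classes could reveal

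*Protocol*

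**What the plan says.** The secondary objective in protocol section 3.2 reads: "To explore the correlation between fecal calprotectin, EPC and EPX levels and histological activity among MC patients".

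Section 9.1 turns this into AUCs. Its general rule is "Area under the ROC curve will be used to correlate numerical variables with binary categorical variables". For histology it takes "The association between fecal calprotectin, EPC and EPX levels with histological features (collagen thickness", inflammation and IEL count) and gives each feature two levels: collagen up to 5 µm or above, Geboes below 3.1 or not, IEL up to 5 per 100 cells or above. These "will be analyzed through Area Under the ROC Curve at each data collection time point (diagnosis and month 24").

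Section 7.1 records finer data at both time points:
- Collagen: "Thickness of the subepithelial collagen layer (not observed", followed by a low class, a class between 5 and 10 µm, and a class from 10 µm up).
- IEL: "IEL in the surface epithelium (not observed, < 5 IEL/100 surface epithelial cells, > 5 and < 20 IEL/100 surface epithelial cells", and a class from 20 up).
- Geboes: a grade for each of five colon segments.

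On numbers, section 9.2 says that "approximately 30 patients with MC are expected to be followed in the prospective component study".

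**The concern.** The objective is a correlation, but the only analysis specified for it asks whether a marker separates tissue below a limit from tissue above it. A patient with 6 µm of collagen and one with 20 µm count as the same. A marker that rises steadily with tissue change is then judged on one contrast.

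The cuts also sit awkwardly in this population at diagnosis, one of only two histology time points. Section 7.4.2 makes IEL above 5 and/or collagen above 5 µm the condition for MC. Every collagenous colitis (CC) patient is therefore in the high collagen level and every lymphocytic colitis (LC) patient in the high IEL level. The low level of a feature can hold only patients who qualified through the other feature, and it may be very small.

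At stake is information that has already been collected in a small cohort. A marker that follows the degree of change could be missed, or its AUC could be too imprecise to read against the 0.75 benchmark.

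**Working it through.** **1. The plan's own figures (section 9.2).** The 95% half-width is 1.96·√(p(1−p)/300).
- p = 0.10: 1.96·√(0.09/300) = 3.39%.
- p = 0.15: 1.96·√(0.1275/300) = 4.04%.

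Both agree with "with an error margin of less than 4.5% and with 95% confidence interval". The MC count is 300 × 0.10 = 30, or 300 × 0.15 = 45 at the upper prevalence. The section gives no precision or power figure for the marker–histology analysis.

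**2. Stored classes against analysed classes.**

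| Feature | Stored (7.1) | Analysed (9.1) |
|---|---|---|
| Collagen | not observed; low; >5 to <10 µm; ≥10 µm | ≤5; >5 µm |
| IEL per 100 | not observed; <5; >5 to <20; ≥20 | ≤5; >5 |
| Geboes | grade per segment | <3.1; ≥3.1 |

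The stored classes have two gaps. An IEL count of exactly 5 has no class at either visit. Collagen of exactly 5 µm has a class at baseline (≤5) but none at month 24 (<5). The rank of the not-observed entry is not stated.

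**3. Precision of the AUC when the low level is small.** The Hanley–McNeil variance is [A(1−A) + (h−1)(A/(2−A) − A²) + (l−1)(2A²/(1+A) − A²)]/(h·l), with h patients in the high level and l in the low level. At A = 0.75 the three terms are 0.1875, 0.0375(h−1) and 0.0804(l−1).
- h = 15, l = 15: (0.1875 + 0.525 + 1.125)/225 = 0.00817, half-width 1.96·√0.00817 = 0.18.
- h = 27, l = 3: (0.1875 + 0.975 + 0.161)/81 = 0.01634, half-width 0.25. The interval runs from 0.50 to 1.00.

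If the true low share is 10%, the chance that fewer than two of 30 patients fall there is 0.9³⁰ + 30·0.1·0.9²⁹ = 0.042 + 0.141 = 18%.

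**4. Power under a graded relation.** All inputs except n are assumptions, because the documents give none: marker and latent histology bivariate normal with correlation ρ from 0.3 to 0.6, two-sided 5% tests, and assumed shares in the low, middle and top classes. The Mann–Whitney (AUC) test on two levels is compared with Spearman on three ordered levels. Loss of power in points at n = 30:

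| Shares (%) | ρ = 0.3 | 0.4 | 0.5 | 0.6 |
|---|---|---|---|---|
| 50/25/25 | 3 | 6 | 7 | 6 |
| thirds | 7 | 11 | 15 | 13 |
| 20/40/40 | 11 | 18 | 24 | 24 |
| 10/45/45 | 15 | 26 | 36 | 43 |

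With thirds, for example, the ordered analysis has 30/48/70/88% power and the split 23/37/56/75%; the losses were rounded separately. With 70/15/15% the loss is only 1 to 3 points. With 5% in the low level it reaches about 60. When 20–60% are in the low level the range is about 2 to 24 points. At n = 45 the direction is the same: thirds lose about 8, 13, 12 and 7 points.

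A six-level scale standing in for Geboes loses 8, 14, 16 and 12 points with half the patients at or above the cut. With 10% at or above it, the losses are 19, 31, 42 and 47.

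**5. Power under a step relation.** If the marker jumps at the cut and is flat on either side, the two-level test is the stronger one, by about 2 to 15 points or somewhat more depending on the shares.

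**The case against.** The cuts are the protocol's own. Section 7.4.2 uses 5 µm, 5 IEL and Geboes 3.1 as the limits of a normal biopsy. They recur in the remission definitions of section 8.3.2, except that LC remission uses 20 IEL. Asking whether a stool marker separates normal from abnormal tissue suits the monitoring purpose in section 2.2. AUC is also the named secondary endpoint in section 8.2. All this stands, and it is why the AUCs should stay. A reader might infer that the split should be replaced as the main analysis; the documents do not support that.

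The analysis is exploratory, with no hypothesis, significance level or power set for it. That stands too: the loss is lost information and not a shortfall against a target.

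The upper limits of 10 µm and 20 IEL are subtype boundaries and not severity grades. An LC patient with thin collagen would rank low on collagen despite full disease, so a pooled correlation partly reflects subtype mix. This is a fair warning about any added correlation and calls for showing it by subtype as well.

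The Geboes table scores separate dimensions, so treating it as one ladder needs a stated rule. Section 2.2 also reports two studies with no correlation between calprotectin and histological grade, so a monotone relation cannot be taken for granted.

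None of this answers the main point. As written, the analysis cannot distinguish a graded relation from a step, although the data to look for one are recorded.

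**Conclusion.** The point holds as a cheap improvement. Section 9.1 limits the marker–histology analysis to two-level cuts while finer ordered classes are stored. At diagnosis the MC definition may leave the low level of collagen or IEL with few patients.

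Under an assumed monotone relation the split lost power in every setting tried. At n = 30 the loss is roughly 2 to 24 points with 20–60% in the low level, and about 1 to 60 over the wider grid. A reader might want one fixed cost, such as 6 to 21 points. That range arises only for particular assumed shares and an AUC of 0.75 at the cut, and the documents give neither the shares nor an effect size. A reader might also infer that the split is always inferior, but a pure step at the cut reverses the ordering. The firm conclusion is qualitative: the plan assumes the step form and provides no way to see the graded one.

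**What to change.** In section 9.1, keep the AUCs at the three cuts as the named secondary endpoints. Add a Spearman or Kendall correlation, with 95% confidence interval, of each marker with the ordered collagen class, the ordered IEL class and the Geboes grade, at diagnosis and at month 24. Show it overall and descriptively by subtype, because the 10 µm and 20 IEL limits also separate CC and LC from incomplete colitis.

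State three conventions with it:
- how the five segments are summarised into one value per patient, including how the Geboes dimensions become one grade;
- where the not-observed entry ranks;
- which class takes a value of exactly 5, worded the same at baseline and month 24.

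The cost is some wording and a few lines of code, with no new biopsy or reading. The drawbacks are more exploratory estimates, ties within the classes, and a coefficient that is less directly clinical than an AUC and cannot be read against the 0.75 benchmark.
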